methods (HPLC, magnetic resonance spectroscopy, mass spectrometry, UV spectrophotometry, etc.). Through these studies there were identified until present time, 27 carotenoids and 8 metabolites in the human body. Generaly, known carotenoids ingested, absorbed and metabolized by humans and found in serum are in number of 35. Lutein is the most important carotenoid present selectively in certain tissues of the human body, mainly at the level of the retina, macula (hence the name) and lens. In tissues and serum it is found together with a carotenoid dihydroxide, it isomer, zeaxanthin.

Lutein, usualy ingested with other nutrients is partly eliminated directly through fecal matters (50-90%) and partially absorbed with the help of food fats. Incorporated in chylomicrons, it enters the blood flow where thanks to its liposolubility, it ties to the lipoprotein molecules (preferable HDL) and so it gets to different organs: liver, breast, colon, cervix, and ocularly, to the lens, iris and retina where, it selectively focuses in its central region (macula). In the cell, it is places in the entire thickness, from the exterior to the interior, in cellular membranes, tiding up to its polar terminal groups by its own membranes.

Lutein and zeaxanthin are present at the level of the umbilical cord and pass through the placental barrier; they are also present in the plasmatic ones, in breast milk and especially in the colostrum.

Concerning the way of administrating it, the lutein presents, through its specific characteristics, an elevated bioavailability after oral administration. The hematic levels of lutein, after providing nutriments rich in carotenoids, are increased with 67% from the 14% observed at beta-caroten.

Published studies proved that the chrono-active form of carotenoids is able to determin a slow release in the intestine offering a better absorption and reducinf the necessity to be assimilated together with food.

Through interdisciplinary and coordinated studies, performed both *in vitro* and *in vivo*, there were identified different action mechanisms; particularly, it was demonstrated a defense mechanism of the tissue function by lutein, which is produced through the neutralization (quench) phenomenon of singlet oxygen and reactive oxygen species (ROS). This action provides the molecule with different activities: an antioxidant function, anti-inflammatory properties, properties which promote anti-tumoral effects, induction of detoxification enzymes and positive effect on proteins promoting the communication between joints (up-regulation).

Recently, there have appeared experimental and chemical data proving that the oxidative stress and harmful actions determined by ROS can play an important role in the pathogenesis of many neurological diseases as Alzheimer, Parkinson in adult and ROP and NEC in newborns.

This is due to the fact that the nervous system is characterized by membranes high in polyunsaturated fats, the first cellular compounds affected by ROS attack being the lipid perioxidation.

A similar mechanism can appear to certain ocular tissues (macula, lens, retina) which, containing high amounts of polyunsaturated fat acids, are more vulnerable than other structures with oxidative degradations induced by ROS.

Due to the fact that carotenoids are amongst the most powerful antioxidants existing in nature, there are being developed new researches concerning the functional role of these substances in preventing neurodegenerative diseases in newborns. For the first time, few researchers have managed to prove that lutein and zeaxanthin have a protecting role against the photostress of the human macula. This demonstration was possible by isolation, identifying the chemical structure and measuring the concentration of lutein and zeaxanthin and their oxidation products from the eyes of the donners.

During the pregnancy, the percentage of fat acids of pregnant women's plasma increases with approximately 51%. The increase refers manly to the concentration of saturated (+ 57%) and monounsaturated (+ 65 %) fat acids, but also polyunsaturated fat acids increase significantly.

Because the polyunsaturated fat acids are very sensitive to oxidation, the modification of their plasmatic levels influences the state of the antioxidant systems on the mother and subsequently to the fetus. Many studies have proved that the increase of the susceptibility to the peroxidation of polyunsatured fat acids on pregnant women is accompanied by an equivalent increase of the tocopherol plasmatic concentrations which, immediately after birth, decrease sharply.

The plasmatic concentrations of antioxidants on newborns, comparative to the mother's were smaller. In the umbilical cord, the levels of tocopherols and carotenoids are significantly smaller that the ones registered in the maternal plasma and the concentration of polyunsaturated fat acids on the newborn is significantly higher and a lot more increased than on the mother.

Furthermore, specific studies showed a growing interest towords the oxidative stress and oxygen reactive species which supposedly accumulate after birth. Many practices usualy used in the delivery room, for example the drugs given to pregnant woman to ease her pain, the newborn's extraction methods, the techniques to minimize body temperature decrease, blocking the umbilical cord and especially the use of oxygen to 100 % or a ventilated room (Room Air, RA) for newborns presenting asphyxia signs, do not always prove to be efficient, but they can also compromise the health of the newborn as a result of a significant increase of free radicals.

Some specific studies have compared the levels of free radicals, highlighted with particular markers, in the plasma of the umbilical cord of newborns with asphyxia treated 100% with oxygen or 21% with oxygen, comparative to a control group of children without asphyxia. The levels of free radicals were significantly increased immediately after birth in all three groups and grew at the two groups of newborns with asphyxia. In the group treated 21% with oxygen, these values decreased and at 28 days after birth, they have reached the same level of the newborns without asphyxia, whereas at the group treated 100% with oxygen the levels of free radicals still remains very high.

Thus, it results that a short exposure of the newborn to 100% oxygen is the cause of an extended oxidative stress state and a consistent increase of free radicals which seem to be involved in different diseases and pathologies during the first months of life, especially in the preterm infant increasing the incidence of ROP, IVH, BPD, NEC and infections significantly.

As a result, it is desirable that the newborn can increase the level of antioxidant protection to reestablish the oxido-reductive balance and to prevent the problems occurred from an extended exposure to high levels of free radicals and oxygen reactive species.

Oxidative stress, as well as in the case of age diseases, is considered one of the main factors which determine the deterioration of the retina. The attempt to maintain a correct balance between oxidant and antioxidant factors can help to prevent or reduce damage to the eyes or other tissues that occur in the newborn, especially preterm.

The premature birth is the most frequent cause of mortality, morbidity and disability. Premature babies have an extremly high risk to develop ocular or neurological lesions. The main complication at visual level that may appear is called retinopathy of prematurity, so called ROP. Oxidative stress is involved in

the etiology of this disease. In fact, premature babies, because of repiratory issues, are oftenly exposed to potentially damaging oxygen concentrations or to phototherapy with high blue light intensity. These therapuetical practices are sources of free radicals.

The lutein and zeaxanthin present in the macular pigment, due to their capacity to absorb blue light and their antioxidant action, could have an important role in protecting the eyes of the newborn against damages produced by intense light.

On adults, different elements suggest a protective action of lutein against photooxidative damage, proved by numerous studies.

The studies performed on babies showed that the levels of carotenoids in the first four / six months of life are much reduced. This is due to the fact that the baby's diet is based exclusively on milk, without any solid elements (as vegetables or green leaves), sole sources of this nutrient. Nevertheless, breast fed babies, in average, present high plasmatic lutein levels than babies fed with prepared milk. Different milk formuli for newborns found at present time on the market are not enriched with this type of carotenoids, thus their content of lutein and zeaxanthin is very low, exceting certain formuli which are not traded in Italy prepared using egg mixes. Breast milk, is thus the only source of lutein for the newborn before ablactation, and breast feeding proves to be of considerable importance as primary source of these micronutrients for the newborn, proper development and visual function protection. Taking into consideration the correlation between the lutein in the blood and breast milk and the reduction of its levels, similar to all carotenoids, in milk, after 6 days from birth, there is already an important contribution of nutriments high in lutein during breast feeding. Such diet enriched in lutein is particularly important especially for the mothers of premature babies or babies having a small weight when born. In fact, premature babies and underwight babies need more nutritive substances essential to a fast grow, because they have not benefit from the contribution of highly nutritive and energetic substances transferred from their mothers during the last weeks of pregnancy. Also, the gastrointestinal and renal functions which are not completely developed reduce the absorption and withhold of important micronutrients, amongst which important antioxidants that protect the newborn from the exposure to high level of free radicals produced excessively at birth and several times as a result of the resuscitation techniques used. Breast feeding is important for the antioxidant contribution to the protection of the newborn and definitely the nutritional state of the mother has subsequently an essention part because it influences the nutrition of the newborn, especially concerning certain solvable nutritive elements, such as lutein and zeaxanthin.

It should be emphasized that in the literature are already present searches and results with the use of lutein / zeaxanthin in the newborn.

The recent Gong work has evaluated the role of lutein / zeaxanthin comparing the data obtained from various studies, including those of Romagnoli, Dani and Manzoni. Furthermore the RCT analysis of Rubin on the subject, it can be concluded that lutein / zeaxanthin are well tolerated and well absorbed from preterm infants also after oral administration.

The extremely interesting result that has emerged although not statistically significant (probably due to the small sample) is that supplementation with lutein / zeaxanthin reduced the incidence and severity of ROP.

Our protocol is born from the idea that given the interesting results of earlier work is considered important to deepen a dosage of at least 1 ml / kg equal to 0,5 mg of lutein and 0.05 mg of zeaxanthin.

It 'important to assess the value of the key markers of oxidative stress biological

antioxidant potential (BPT) and total hydroperoxide (TH) during and after treatment.

Already in a previous work (S. Perrone, M. Longini) has demonstrated a reduction in radicalemia in term infants, during and after administration of lutein / zeaxanthin by determination of the BTP and TH.

Preparation based on lutein ans zeaxanthin have never reveled on humans negative or harmful effects after administration, or to the gastrointestinal or sistemis level. In recent studies there were not reported adverse phenomena after administrating 20 mg/day of lutein or zeaxanthin for a period of 6 months, or interactions with other liposovable nutritive elements.

Justifying the noncommercial character of the study

This study is based on the administration of a dietary supplement of lutein/zeaxanthin. It is included in the category of a spontaneous/non-commercial pilot study, because it is born from the need of private healt care of identifying a natural antioxidant product which may reduce the severeness of the diseases related to the prenatal period, limiting the sufferance of newborns and their families, by reducing simultaneously the charges in SSN pregnancy which arise from the standard treatments and short-term and medium to long-term rehabilitation.

It was chosen the product *LUTEIN ofta 0,5 gocce*, because Sooft Company proved to be able to supply this drug without any charges, also signing a statement that certifies the fact that the scientific results of the research will remain at the disposal of the scientific community and that the management of the intellectual property protection activity concerning any invention that may derive from the research is made according to the law in force and mainly to Art. 65 of the Executive Decree no. 30 from 10 February 2005 – "The Code of Industrial Property". In conclusion the results of the research will remain available for the Scientific Community and shall not be used for commercial purposes or profit.

The registration and trading status of the product participating at the study

The Registers of the Ministry of Health concerning non-pharmacological products The product is registeres in the Register of dietary supplements on the web site of the Ministry of Health (http://www.ministerosalute.it/alimenti/dietetica) and classified with the following code: 905619452, according to the executive decree no. 111 from 27 January 1992. These products are submitted to the European Directive concerning food, according to the Executive Decree no. 169 from 21/05/2004, and to the European Directive 2001/20/EC concerning drugs, transposed to Italian level throyh the executive decree 211 from 24/06/2003.

Ingredients: solution of 5% Lutein and 2,25% Zeaxanthin with excipients (Corn starch, glucose, potassium sorbate, xanthan gum, citric acid).

Description: LUTEIN ofta 0,5 gocce is a dietary supplement based on lutein and zeaxanthin.

The lutein and its isomer, zeaxanthin, are two carotenoids highly spreaded in nature, which cannot be synthetized by the human body. They are normaly absorbed through food rich in such carotenoids (vegetables with green leaves, with big leaves as turnips and spinach, and fruits such as apricots and kiwi) and through breast milk. After absorption, the lutein and zeaxanthin are distributed to all tissues, but they are selectively accumulating in the eyes. Mainly, they are focusing in the retina and macula lutea, the latter being the place where clear images are formed, whose development is complete around the 4th or 5th month of life. The lutein and zeaxanthin are the only pigments present at the level of macula lutea and have a protection role.

They contribute and maintain the functionality and integrity of the eye's sensitive structures (retina, iris, lens), preventing or reducing the damages caused by free radicals. In specialized literature is largely described their high antioxidant

	activity and the advantages of a consumption or supplement. Lutein and zeaxanthin pass through the placental barrier, they are also present in the colostrums and breast milk and it is believed that they take part to the embryogenesis of the retina and to the development of visual functions during the first weeks of life. As a result, the lutein and zeaxanthin are essential to the health of the eye, both on adults and children suring their first hours of life. Thus, the absorption of these substances proves to be necessary in situations of necessity growth or in case of deficient intake, both during the aging period of the ocular structures responsible for the visual function (macula), and during their conservation period. The lutein and zeaxanthin do not present contraindications and can be taken at any age. Use: LUTEIN ofta 0,5 gocce is indicated in situations of necessity growth or in case of deficient food intake of its components on different age groups. LUTEIN ofta 0,5 gocce can be useful especially in preventing macular or retina damages.	
Study Objectives	Main objective	
, and a second s	To evaluate if the administration of pharmacology doses of Lutein/Zeaxanthin micronutrients in water (LUTEIN ofta 0,5 gocce – Neoox) is able to reduce the level of radicalemy and at the same time to elevate the antioxidant power of premature newborns (gestational age: \leq of 32 weeks and / or weight at birth: \leq 1500 grams).	
Study scketch	pilot study, non-commercial, with food supplement, treated vs. control with a	
	ratio 1: 1 double-blind. The identical vials, corresponding to placebo and active product, have an alphanumeric code without meaning for the operator, but that identifies the traty from control, in an anonymous document kept by the Statistical. The document will be placed in a sealed and anonymous envelopeand it will be kept open by the statistician at the time of data analysis.	
People	Inclusion criteria	
participating at	• Newborns with a weight ≤ 1.500 grams and/or gestational age ≤ 32 weeks;	
the study and their number	Male and female newborns; Newborns where reports went to sign the information forms informed.	
number	• Newborns whose parents want to sign the information form – informed consent.	
	Consent	
	Exclusion criteria	
	• Informed consent is not signed	
	 Infants of birth weight ≥ 1.500 gramms and/or gestational age > 32 weeks infants hospitalized after 36 hours of life 	
	Infants with ophthalmologic disease at randomization	
	• infants with severe malformations	
	Number of nationts about to be varietaved	
	Number of patients about to be registered It is expected to register a total number of 50 newborns divided in two groups:	
	• Experimental group A: 25 newborns treated;	
	Control group B: 25 newborns treated.	
Randomization	Subsequently enrollment patients will be randomly divided into Group A and Group B throught a web system that allows the randomization into three different recruitment centers	

	T
Number of centres	Multicenter pilot study. At the study will participate three Italian experimental centres: Naples, Siena and
	Padova.
	The centre from Naples will be the national coordinator and the center from Siena
	will handle in a centralized way the laboratory results. The center from Padova
	will help to recruit an adequate number of cases.
Sample size	BAP and TH are two bio-markers with different hypothetical changes clearly different. For this reason we will use the study method proceeds by the following online site http://clincalc.com/stats/samplesize.aspx (Rosner B. Fundamentals of Biostatistics. 7th ed. Boston, MA: Brooks/Cole; 2011). The inserted reference values are for BAP 2361 (\pm 466) μ mol/L and for TH 156.75 (\pm 64.0) Ucarr (Perrone S., Longini M. et. Al). The difference for BAP that we hypothesize to find is an increase of at least 500 μ mol / L which is approximately 20% of the control data. By setting α = 0.05% and β =0.1% with a power of 90% the number of samples required is 25 + 25 = 50. For the TH assume a decrease of 50 Ucarr which is approximately 30% of the
	data of the control. By setting $\alpha = 0.05\%$ and $\beta = 0.2\%$ with a power of '80% also in this case the required number of samples is $25 + 25 = 50$.
	However $25 + 25$ is the minimum number. Taking into account any ongoing study waivers (parents may request to discontinue treatment at any time) which go beyond statistical calculations. So in case of necessity we will recruit a number of infants to reach the minimum number according to the design of the protocol (25 $+$ 25).
Treatment and	Products administered:
Treatment and dosage	Products administered: LUTEIN ofta 0,5 gocce, containing a solution of 5% Lutein and 2,25% Zeaxanthin with excipients (Corn starch, glucose, potassium sorbate, xanthan gum, citric acid) (group A) Placebo solution with unique excipients (Demineralised water, potassium sorbate, xanthan gum, citric acid) (group B) Experimental Group: Group A (25 newborns) will be treated with LUTEIN ofta 0,5 gocce, (1 ml per Kg equal to 0,5 mg of lutein and 0,05 of zeaxantin), divided in two additional administrations during the day from the standard hospital treatment foreseen. The
	Products administered: LUTEIN ofta 0,5 gocce, containing a solution of 5% Lutein and 2,25% Zeaxanthin with excipients (Corn starch, glucose, potassium sorbate, xanthan gum, citric acid) (group A) Placebo solution with unique excipients (Demineralised water, potassium sorbate, xanthan gum, citric acid) (group B) Experimental Group: Group A (25 newborns) will be treated with LUTEIN ofta 0,5 gocce, (1 ml per Kg equal to 0,5 mg of lutein and 0,05 of zeaxantin), divided in two additional administrations during the day from the standard hospital treatment foreseen. The first dose will be given within 36 hours of life, the least to 30 th day of life. Control Group: Group B (25 newborns) treated with Placebo solution (additionaly to the standard hospital treatment foreseen. The first dose will be given within 36 hours of life,
	Products administered: LUTEIN ofta 0,5 gocce, containing a solution of 5% Lutein and 2,25% Zeaxanthin with excipients (Corn starch, glucose, potassium sorbate, xanthan gum, citric acid) (group A) Placebo solution with unique excipients (Demineralised water, potassium sorbate, xanthan gum, citric acid) (group B) Experimental Group: Group A (25 newborns) will be treated with LUTEIN ofta 0,5 gocce, (1 ml per Kg equal to 0,5 mg of lutein and 0,05 of zeaxantin), divided in two additional administrations during the day from the standard hospital treatment foreseen. The first dose will be given within 36 hours of life, the least to 30th day of life. Control Group: Group B (25 newborns) treated with Placebo solution (additionaly to the standard
dosage	Products administered: LUTEIN ofta 0,5 gocce, containing a solution of 5% Lutein and 2,25% Zeaxanthin with excipients (Corn starch, glucose, potassium sorbate, xanthan gum, citric acid) (group A) Placebo solution with unique excipients (Demineralised water, potassium sorbate, xanthan gum, citric acid) (group B) Experimental Group: Group A (25 newborns) will be treated with LUTEIN ofta 0,5 gocce, (1 ml per Kg equal to 0,5 mg of lutein and 0,05 of zeaxantin), divided in two additional administrations during the day from the standard hospital treatment foreseen. The first dose will be given within 36 hours of life, the least to 30th day of life. Control Group: Group B (25 newborns) treated with Placebo solution (additionaly to the standard hospital treatment foreseen. The first dose will be given within 36 hours of life, the least to 30th day of life. The product will be administered by adding it in the milk (human or formulae), or
Way of intake Duration of the period of	Products administered: LUTEIN ofta 0,5 gocce, containing a solution of 5% Lutein and 2,25% Zeaxanthin with excipients (Corn starch, glucose, potassium sorbate, xanthan gum, citric acid) (group A) Placebo solution with unique excipients (Demineralised water, potassium sorbate, xanthan gum, citric acid) (group B) Experimental Group: Group A (25 newborns) will be treated with LUTEIN ofta 0,5 gocce, (1 ml per Kg equal to 0,5 mg of lutein and 0,05 of zeaxantin), divided in two additional administrations during the day from the standard hospital treatment foreseen. The first dose will be given within 36 hours of life, the least to 30th day of life. Control Group: Group B (25 newborns) treated with Placebo solution (additionaly to the standard hospital treatment foreseen. The first dose will be given within 36 hours of life, the least to 30th day of life. The product will be administered by adding it in the milk (human or formulae), or in a small quantity of glucose, either orally or by gavage. The administration of the product (LUTEIN ofta 0,5 gocce) starts within the first
Way of intake Duration of the period of administration	Products administered: LUTEIN ofta 0,5 gocce, containing a solution of 5% Lutein and 2,25% Zeaxanthin with excipients (Corn starch, glucose, potassium sorbate, xanthan gum, citric acid) (group A) Placebo solution with unique excipients (Demineralised water, potassium sorbate, xanthan gum, citric acid) (group B) Experimental Group: Group A (25 newborns) will be treated with LUTEIN ofta 0,5 gocce, (1 ml per Kg equal to 0,5 mg of lutein and 0,05 of zeaxantin), divided in two additional administrations during the day from the standard hospital treatment foreseen. The first dose will be given within 36 hours of life, the least to 30th day of life. Control Group: Group B (25 newborns) treated with Placebo solution (additionaly to the standard hospital treatment foreseen. The first dose will be given within 36 hours of life, the least to 30th day of life. The product will be administered by adding it in the milk (human or formulae), or in a small quantity of glucose, either orally or by gavage. The administration of the product (LUTEIN ofta 0,5 gocce) starts within the first 36 hours of life and continues with daily administration for 30 days.
Way of intake Duration of the period of administration	Products administered: LUTEIN ofta 0,5 gocce, containing a solution of 5% Lutein and 2,25% Zeaxanthin with excipients (Corn starch, glucose, potassium sorbate, xanthan gum, citric acid) (group A) Placebo solution with unique excipients (Demineralised water, potassium sorbate, xanthan gum, citric acid) (group B) Experimental Group: Group A (25 newborns) will be treated with LUTEIN ofta 0,5 gocce, (1 ml per Kg equal to 0,5 mg of lutein and 0,05 of zeaxantin), divided in two additional administrations during the day from the standard hospital treatment foreseen. The first dose will be given within 36 hours of life, the least to 30th day of life. Control Group: Group B (25 newborns) treated with Placebo solution (additionaly to the standard hospital treatment foreseen. The first dose will be given within 36 hours of life, the least to 30th day of life. The product will be administered by adding it in the milk (human or formulae), or in a small quantity of glucose, either orally or by gavage. The administration of the product (LUTEIN ofta 0,5 gocce) starts within the first 36 hours of life and continues with daily administration for 30 days. Duration of the observation period of the patient registered

laboratory investigations foreseen. The second semester will be used to study and analyse the results achieved.

Procedures

Methodology:

When born, premature newborns that are comply with the inclusion parameters will be introduced and separated in two random groups (A and B).

All newborns, during the observation period, will be submitted to the blood collection (1 ml) from the umbilical cord and peripheral (at the same time with the routine collections) on which there will be performed blood gas analysis and oxidative stress markers (TH and BAP). All registered newborns will also be submitted to the verification of their history concerning the examination and collection, in view of evaluation the presence or absence of ROP, NEC, IVH, BPD and infections.

Collection Time

- T0, basic at birth, before begining the treatment: blood collection from the umbilical vein.
- T1, first check, to 15 days after initiation of treatment: peripheral blood collection in view of verifying it before the Lutein/zeaxanthin administration.
- T2, second check, at 30th day since the begining of treatment: peripheral blood collection in view of verifying it before the Lutein/zeaxanthin administration.

The parents will be informed concerning the experimental procedure and the checks schedules.

It will be required the written consent of the parents.

The protocol shall be submitted to approval to the local ethics commission.

Evaluation Parameters:

Efficiency:

a) Evaluation of oxidative stress biomarkers in the peripheral blood of the premature newborn before and after the treatment.

Tolerability:

There will be transcribed on the data sheet possible adverse events which may be observed by the doctor.

Evaluation Scale

- a) Evaluation of the oxidative stress: by deremining the oxidative stress biomarkers and registering them in the data sheet.
- b) They must be indicated:

Demographic Characteristics

- Sex
- Gestational Age
- Weight (with percentile)
- Mode of delivery
- Preeclampsia
- Premature rupture of membranes
- Using steroids before birth
- Using antibiotics before birth
- Use of drugs or harmful substance before birth

Clinical features

	 Apgar score Use of surfactant Umbilical catheter CVC location and duration Intubation Mechanical ventilation (procedures and time) Supplementation of O2 Incidence of infections Use and type of antibiotics Use and type of antifungal Use and type of post-natal steroids Use and type inotropic Use of NPT Duration of treatment in NICU Nutritional Characteristics: Oral feeding start time Exclusive oral feeding start time Fluid volume Intake calories (protein, carbohydrates and fats) Use of maternal and /or uman milk Other therapies associated and/or permitted During the trial period it is not permitted any product administration or antioxidant activities (anti-radicals) or products which contain even a sole
Basic examination	component having this result, excepting the protocol. At birth, as it is foreseen by newborn protocols, the babies will be submitted to
	several medical examinations.
Control examination	From the Birthing Unit, the newborns will be transered to intensive care rooms where they will be submitted to multiple control examinations.
Follow-up examinations	As it is foreseen in neonatal protocols.
Statistical Analysis	The Student t test for independent data is the type of analysis that will be used to assess statistically significant differences between the parameters recorded in the two groups (treated and control). The Student t test is the method of choice for analysis as it allows to evaluate the values of a continuous random variable measured in not very many samples (25 subjects per group). It will be using the statistical package SPSS system.

REFERENCES

Lutein: description, pharmacokinetics activity and characteristics, mechanism of action, safety and tolerability

- 1. Shao, A. and Hathcock, JN. Risk assessment for the carotenoids lutein and lycopene. Regul Toxicol Pharmacol. 2006 Aug;45(3):289-98.
- 3. Khachik F, de Moura FF, Chew EY, Douglass LW, Ferris FL 3rd, Kim J, Thompson DJ. The effect of lutein and zeaxanthin supplementation on metabolites of these carotenoids in the serum of persons aged 60 or older. Invest Ophthalmol Vis Sci. 2006 Dec;47(12):5234-42.

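### The statistician who holds the treatment key opens it for the analysis, with no requirement that the data be locked or the open analysis choices fixed first

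*Combined protocol and SAP*

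**What the plan says.** The Study scketch section describes the trial as "ratio 1: 1 double-blind". Active and placebo vials look identical and "have an alphanumeric code without meaning for the operator". The link from code to treatment is "in an anonymous document kept by the Statistical", in a sealed envelope. On opening, the text says "it will be kept open by the statistician at the time of data analysis". The English is rough, but the natural meaning is that the statistician opens the envelope when the analysis takes place.

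The Statistical Analysis section is three sentences long. It says "The Student t test for independent data is the type of analysis that will be used", applied to "differences between the parameters recorded in the two groups (treated and control" arms, with SPSS as the software. Under Procedures, efficacy is "Evaluation of oxidative stress biomarkers in the peripheral blood of the premature newborn before and after the treatment", with samples at T0 (cord blood), T1 (15 days) and T2 (30 days). The Sample size section sizes the trial separately on BAP and on TH. It expects some parents to withdraw their infants and recruits further infants until 25 + 25 is reached.

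**The concern.** The key-holder and the analyst appear to be the same role, and opening is tied to the analysis rather than to any completed step. If the analysis were fully specified, this would matter little. Here several decisions that can move the result are still open at that moment, and the protocol entitles the person making them to know which infants received lutein. If one biomarker result came out significant, a reader could not rule out that the marker, visit, scale or analysis set had been settled with the arms in view. With 25 infants per arm and no ranking of the outcomes, that doubt could not be answered afterwards.

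**Working it through.** The plan gives no figure on this point, so there is none to reproduce. The check has two parts: the order of events, and the room that the open choices leave.

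**1. Order of events**

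| Step | What the protocol requires before the envelope is opened |
|---|---|
| Enrolment, dosing, sampling, assay | Key sealed; operator blind (Study scketch) |
| Database lock | Not mentioned |
| Blind data review | Not mentioned |
| Dated analysis plan | Not mentioned |
| Comparison on neutral labels | Not mentioned |

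**2. What is still open**

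- Marker: BAP and TH are each powered (Sample size); no ranking or multiplicity rule.
- Time point: T1 or T2 (Procedures); neither is named as primary.
- Scale: level, or change from T0. The efficacy wording is before-and-after, but the test is a between-group comparison of recorded values.
- Analysis set: infants who stop are replaced; whether they are still analysed is not stated.
- Missing samples, outliers, transformation: no rule.

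The first three items alone give 2 × 2 × 2 = 8 versions of the test, four per marker.

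**3. Room left by time point, scale and marker**

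Inputs: 25 per arm (Sample size) and a pooled two-sided t test on 25 + 25 − 2 = 48 degrees of freedom. The level is 5%, which is an assumption because the protocol prints 0.05%. T0, T1 and T2 are taken as normal with equal correlation ρ within infant; ρ is also an assumption, since the documents give no value.

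If the versions were independent, the chance of at least one p < 0.05 under no effect would be 1 − 0.95^k:

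- k = 4: 1 − 0.95⁴ = 18.5%
- k = 8: 1 − 0.95⁸ = 33.7%

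The versions are correlated, so simulation under no effect gives somewhat less:

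| Null simulation | One marker (4 versions) | Either marker (8 versions) |
|---|---|---|
| 20,000 trials, ρ = 0.3 / 0.5 / 0.7, markers independent | 15.9% / 15.8% / 16.0% | 29.6% / 29.4% / 29.3% |
| 40,000 trials, ρ = 0.2 / 0.5 / 0.7, markers independent | 15.8% / 16.2% / 15.9% | 29.3% / 30.0% / 29.4% |
| As the row above, markers correlated −0.5 | 16.0% / 16.0% / 16.1% | 27.5% / 27.5% / 28.0% |

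Arithmetic check for independent markers: 1 − (1 − 0.16)² = 29.4%. Choosing only between T1 and T2 levels for one marker gives 8% to 10%.

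**4. The part that knowing the arms lets an analyst aim for**

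Counting only significant results in the hoped-for direction (BAP up, TH down), the 40,000-trial simulation gives about 8% for one marker. For either marker it gives 15.4% to 16.0% with independent markers and 14.2% to 14.5% with correlation −0.5. Check: 1 − (1 − 0.08)² = 15.4%.

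**5. What neutral labels change**

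Swapping the arm names changes the sign of t but not |t|, so the two-sided p-value is the same. An analyst choosing among the eight versions on coded groups reaches the same 16% and 30%. What brings the error back is fixing one version beforehand: a single pre-chosen test simulates at 4.9% to 5.1%.

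**The case against.** The strongest reply is that the text promises blinding of the operator, keeps the key sealed until analysis, and sets aside a second semester for analysing results, which suggests that collection and assays come first. On that view the double-blind label is honoured and only a wording gap remains. Much of this stands. A reader might infer that the blind is broken during the trial; the documents do not support that. Nor do they say that exclusions or cleaning follow the opening. That is an inference from the missing lock and the open choices.

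A second reply is that the percentages measure unspecified endpoints, not unblinding. This also stands. A reader might infer that running the comparison on coded groups would by itself remove the inflation. It would not, as step 5 shows.

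A third reply concerns the either-marker figure. The main objective asks for lower radical levels and higher antioxidant power together. If success required both, the one-marker figure would give 0.16 × 0.16 = 2.6% with independent markers. But the protocol states no success rule, so that reading is not secured. Expressing the assumed differences as percentages of control values hints at levels rather than changes, but it does not fix the scale or the visit.

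Finally, a reader might suppose that the vial codes already split the infants into two anonymous groups. The documents do not say whether codes are per group, per vial or per infant. The labels A and B cannot serve either, because the protocol defines them openly: "Experimental group A: 25 newborns treated".

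**Conclusion.** The point holds for the analysis stage. The protocol states when the key is opened and by whom, and nothing requires the data or the analysis to be settled first. Marker, time point, scale, analysis set and missing samples can therefore be decided with treatment known.

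The illustrated size, under no effect with 25 per arm and assumed within-infant correlations of 0.3 to 0.7, is about 16% for one marker and about 30% for either marker, against a nominal 5%. In the direction favouring treatment it is about 8% and 16%. These figures come from the unfixed choices. They are not an upper bound, because cleaning, exclusions and missing samples are left out, and they are not an estimate of actual bias, because nothing shows that the freedom would be used.

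The matter does not invalidate the design or alter the sample size. It should be corrected before any comparison by group.

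**What to change.** Replace the last sentence of the design text in Study scketch by:

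> The envelope stays sealed until (1) the analysis of TH and BAP (marker, time point, level or change, analysis set, missing samples) is fixed in writing and dated, before any comparison by group, and (2) the database is locked after a review blind to treatment. The planned tests are then run on two neutral group labels (not A/B), prepared by someone other than the analysing statistician, for example the administrator of the web randomisation system. The envelope is opened afterwards to attach treatment names.

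Item (1) is what restores the error rate. The lock and the neutral labels keep data decisions from being made with treatment known. The protocol already has a web randomisation system, so a separate person to prepare the labels should be available.

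The cost is protocol wording, a dated lock note and a short delay before treatment names are attached. No further infants, blood samples or assays are needed.
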